14.1 Collection and reporting of adverse events

AEs¹ will be collected from time of first dosing of IMP until completion of the clinical trial. At all visits, the subject will be asked a non-leading question by the investigator about AEs, for example: "How have you felt since I saw you last?" No specific symptoms will be asked for. It is important that the investigator also observes the subject for any changes not reported by the subject and records these changes.

SUSARs (Suspected, Unexpected Serious Adverse Reactions²) will be immediately reported directly to the Danish Medicines Agency in accordance with Danish legislation.

All SAEs³ (Serious Adverse Events) and applicable AEs will be recorded in the medical record and the eCRF.

Section 4.8 in the Product Information (appendix I) serves as reference for determining the relevance of events/reactions.

It is the responsibility of the investigators to forward an annual safety report including a list of SAEs to the Ethical committee and the Danish Medicines Agency.

All serious adverse reactions (SARs) from the entire trial must appear from the annual report on the trial subjects' safety. This includes expected as well as unexpected serious adverse reactions (SARs and SUSARs)

All important adverse events from the trial must appear from the final reporting of trial results in the EudraCT database in accordance with the [EU guideline 2008/C168/02](#).

Trial ID (EudraCT No.): 2017-003697-14	Date: 23.02.2018	Page Version 2.3
---	------------------	---------------------

¹ Adverse event: Medical occurrence temporally associated with the use of a medicinal product, but not necessarily causally related

²Adverse reaction: All untoward and unintended responses to an investigational medicinal product related to any dose administered.

- The definition covers also medication errors and uses outside what is foreseen in the protocol, including misuse and abuse of the product.
- The definition implies a reasonable possibility of a causal relationship between the event and the IMP. This means that there are facts (evidence) or arguments to suggest a causal relationship.
- An untoward and unintended response to a non-IMP which does not result from a possible interaction with an IMP is, by definition, not a SUSAR

'Serious' adverse reaction:

Regarding the criterion of 'seriousness', reference is made to footnote 3.

³An SAE is any untoward medical occurrence that

- results in death.
- is life-threatening.
- requires inpatient hospitalisation or prolongation of existing hospitalisation. (Planned hospitalisation or planned prolonged hospitalisation do not fulfill the criteria for being an SAE but should be documented in the subject's medical record).
- results in persistent or significant disability/incapacity.
- is a congenital anomaly/birth defect.
- is a medically important condition. Events that may not be immediately lifethreatening or result in death or hospitalisation but may jeopardise the subject or may require intervention to prevent one of the other outcomes listed in the definition above. Examples are intensive treatment in an emergency room or at home for allergic broncospasm, blood dyscrasias and convulsions that do not result in hospitalization, development of drug dependency or drug abuse.

15 Statistical methods

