Suicidal ideation and behavior, including 4 completed suicides, occurred in subjects treated with brodalumab in the psoriasis clinical trials. There were no completed suicides in the 12-week placebo-controlled portion of the trials. Brodalumab users with a history of suicidality or depression had an increased incidence of suicidal ideation and behavior as compared to users without such a history. A causal association between treatment with brodalumab and increased risk of suicidal ideation and behavior has not been established.

Brodalumab is contraindicated in patients with active Crohn's disease and should be used with caution in patients with a history of Crohn's disease because brodalumab may cause worsening of disease.

Further details are available from the product description (Appendix I).

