8.9 Benefit/risk assessment

There is an unmet medical need to reduce the increased risk of cardiovascular disease in patients with psoriasis. Cardiovascular disease caused by premature atherosclerosis is the cause of morbidity and decreased quality of life as well as increased mortality in patients with psoriasis. Due to the high prevalence of the disease this is relevant to a large number of patients. Brodalumab targets IL-17RA which has been shown as a key receptor in psoriasis patogenesis and a promising target in atherosclerosis.

Brodalumab has already demonstrated high efficacy and a favorable safety profile in the treatment of moderate-to-severe psoriasis in clinical studies. The drug is approved for the treatment of moderate-to-severe psoriasis by EMA and DMA.

In order to ensure appropriate treatment of the patients after they have completed the trial, the subjects will be treated at the investigator's discretion or referred to other physicians according to clinical practice and national treatment guidelines.

In patients undergoing FDG-PET/CT, it is well known that incidental focal lesions can be indicative of premalignant or malignant lesions. For instance, studies have shown that FDG-PET/CT reveals unexpected colonic FDG uptake in approximately 5% of patients and that a considerable number of these are diagnosed as premalignant or malignant.⁴⁷⁻⁴⁹

A high frequency of incidental PET findings have previously been shown in psoriasis patients.⁵⁰

We found incidental focal colorectal FDG-uptake in one of 12 cases in our pilot study of aortic vascular inflammation in patients with moderate-to-severe psoriasis.³⁴ This particular case of asymptomatic colorectal cancer was diagnosed earlier than would have been the case if the patient had not undergone FDG-PET/CT. The cancer was curably removed by surgery.

In the current study, the low-dose FDG-PET/CT protocol will limit the area of interest to the thoracic and upper abdominal area.

The main risk in this study is associated with the exposure to radiation. A low radiation dose PET protocol and a limited non-enhanced CT protocol has been adopted to reduce the radiation dose to a minimum without sacrificing data quality.⁵¹

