11.3 Exclusion criteria

1. Non-Danish speaking
2. Known or suspected allergy or reaction to any component of the IMP formulation.
3. History of inflammatory bowel disease, arthritis (not including psoriatic arthritis), systemic lupus erythematosus, and active inflammatory skin diseases.
4. A history of malignancies within the past five years (excluding localized non-melanoma skin cancer).
5. Topical corticosteroid treatment (class III or stronger) and/or ultraviolet type B phototherapy within 2 weeks prior to randomization
6. Treatment with psoralen plus ultraviolet type A photochemotherapy, methotrexate, cyclosporine, acitretin, or fumaric acid esters within 4 weeks prior to randomization.
7. Treatment with adalimumab, etanercept, infliximab, cosentyx, or ixekizumab within 12 weeks, ustekinumab within 24 weeks, or other immunosuppressive or anti-inflammatory agents within 5 half-lives of the active substance prior to the FDG-PET/CT, respectively.
8. Scheduled surgery during the trial period (expect minor minimally invasive procedures).
9. Systemic infection or fever within 7 days prior to FDG-PET/CT.
10. Severe obesity (> 150 kg due to a PET/CT scanner limitation).

Trial ID (EudraCT No.): 2017-003697-14	Date: 23.02.2018	Page Version 2.3
---	------------------	---------------------

11. Presence of uncontrolled diabetes mellitus (HbA1c > 75 mmol/mol and/or blood sugar > 11.1 mmol/l and/or clinical judgment).
12. History of coagulation defects (clinical judgment).
13. Active or latent tuberculosis requiring treatment.
14. Positive hepatitis B surface antigen (HBsAg), hepatitis B surface antibody (HBsAb), hepatitis B core antibody (HBcAb) or hepatitis C virus antibody (anti-HCV) serology at screening. Subjects with positive HBsAb may be randomised provided they are hepatitis B vaccinated and have negative HBsAg and HBcAb.
15. History of any known primary immunodeficiency disorder including a positive human immunodeficiency virus (HIV) test at screening, or the subject taking antiretroviral medications as determined by medical history and/or subject's verbal report.
16. No history of varicella zoster infection and negative varicella antibody test (until varicella vaccination is completed).
17. History of chronic alcohol or drug abuse within 12 months prior to screening, or any condition associated with poor compliance as judged by the investigator.
18. History of intravenous drug use.
19. History of attempted suicide or is at significant risk of suicide.

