13.2.2 Medical history

Relevant past and concurrent medical history must be recorded and includes:

- Psoriasis medical history: all past and current history including:
 - Duration of psoriasis in years
 - Severity of psoriasis
 - Previous psoriasis treatments
 - Psoriasis clinical manifestations (plaque, scalp, nails, genital/flexural)
 - Family history of psoriasis
 - Co-morbidities including psoriatic arthropathy*, obesity, diabetes mellitus, arterial hypertension, hypercholesterolemia, stroke, ischemic heart disease, and depression
- Other medical and surgical history including concurrent diagnoses.

Relevant medical history includes also diseases which are specifically listed as exclusion criteria and diseases for which specific treatments are listed as exclusion criteria.

*Psoriatic arthropathy: history of formal psoriatic arthritis diagnosis or; pain, stiffness for >30 minutes in the morning / after prolonged inactivity. Improves with activity. Peripheral or with axial involvement – inflammatory back pain and stiffness that improve with activity. Night symptoms.

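### The protocol describes a suicidality signal raised by depression history and admits subjects with stable depression history, but plans no targeted on-treatment enquiry; detection rests on one open question and observation at weeks 6 and 16

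*Protocol*

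**What the plan says.** **The risk.** Protocol Section 8.4 states: "Suicidal ideation and behavior, including 4 completed suicides, occurred in subjects treated with brodalumab in the psoriasis clinical trials". It goes on: "Brodalumab users with a history of suicidality or depression had an increased incidence of suicidal ideation and behavior". The same paragraph carries two qualifications: "There were no completed suicides in the 12-week placebo-controlled portion of the trials" and "A causal association between treatment with brodalumab and increased risk of suicidal ideation and behavior has not been established".

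**Who may enter.** Section 11.3, exclusion 19, reads: "History of attempted suicide or is at significant risk of suicide". Exclusion 24 removes psychiatric disorders that the investigator considers unstable and that could affect safety, findings or completion. Depression as such is not an exclusion. Section 13.2.2 lists it among the comorbidities to record: "hypercholesterolemia, stroke, ischemic heart disease, and depression".

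**How events are found on treatment.** Section 14.1 has the investigator put a non-leading question about adverse events at every visit, and adds: "No specific symptoms will be asked for". The sentence after that asks the investigator also to watch for, and record, changes the subject does not mention.

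**When.** The Section 7 schedule ticks adverse event collection at visit 3 (week 6) and visit 4 (week 16). It has no row for mood or suicidality. Under Section 12.2, doses after the first are normally given at home.

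**The concern.** The background section names a psychiatric signal and a group in whom it was more frequent. The eligibility rules let part of that group in. The rule for eliciting adverse events then makes no provision for the signal. An open question is a reasonable way to pick up an injection-site reaction or a cold. It is poorly suited to suicidal thoughts, which many people do not raise unprompted and which an examiner may not see.

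Two things are at stake. The first is the safety of individual subjects: ideation that could have been noticed at a scheduled visit may pass unrecorded. The second is the safety record itself: an adverse event table showing no ideation would be hard to read, because it could not be separated from the fact that nobody was asked.

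**Working it through.** The point turns on what the sections say when set side by side.

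1. **Is the signal the protocol's own?** Yes. Section 8.4 reports it, including 4 completed suicides, and names a history of suicidality or depression as the setting of higher incidence. It claims no causal link.

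2. **Can subjects from that group be randomised?** In part. Exclusion 19 removes those with a past attempt or significant risk. Exclusion 24 removes those with an unstable disorder. What remains is a history of depression judged stable and without significant suicide risk. Section 13.2.2 expects such subjects, since it records the condition. The schedule ticks eligibility only at screening (week -4), so no judgement of suicide risk is scheduled after dosing starts.

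3. **Which scheduled on-treatment routes could reveal ideation?**
   - The open question in Section 14.1: only if the subject raises it.
   - Investigator observation in Section 14.1: only if something is visible.
   - DLQI (Section 13.3.2.1): described as covering the impact of skin disease on quality of life.
   - PSI (Section 13.3.2.2): eight skin symptoms.
   - VAS (Section 13.3.2.3): joint pain.
   - Subject's administration log (Section 12.7.5): date and site of injection.

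   None of these, as described in the protocol text, asks about low mood or suicidal thoughts.

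4. **How often do the first two routes operate on schedule?** Twice after the first dose, at weeks 6 and 16. The gaps are 6 - 0 = 6 weeks and 16 - 6 = 10 weeks. With dosing at weeks 0, 1 and 2 and every other week after that, the doses due from week 6 up to the final visit are those of weeks 6, 8, 10, 12 and 14: five doses, normally at home.

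5. **Does the protocol use targeted enquiry elsewhere?** Yes. Section 12.2 tells subjects to make contact if they have fever before an injection or scan, and the PSI and VAS ask directly about named symptoms. A directed question is therefore not foreign to this design.

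6. **Can missed cases be counted?** No. The documents give no rate of ideation, no expected number of subjects with a depression history, and no detection rate for an open question. Any figure would be assumed throughout.

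**The case against.** The best case for the protocol has several parts.

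- **Open questioning is ordinary practice.** It is the same in both arms and avoids prompting. This stands. The sentence in Section 14.1 describes how adverse events are elicited; it does not stop an investigator from enquiring clinically when something is noticed. Section 13.1 also allows unscheduled visits with assessments at the investigator's discretion. The gap is the lack of a targeted item beside the open question, and calling Section 14.1 a ban on enquiry would over-read it.
- **Observation is a second route.** This stands too. A reader might infer that ideation would come to light only if volunteered. The next sentence of Section 14.1 contradicts that. Observation at two visits is a weak route to unspoken thoughts, but it is a stated one.
- **Entry is already restricted.** Exclusions 19 and 24 together take out the subjects of most obvious concern. What is left is a narrower group of unknown size.
- **The signal is qualified.** Causality is not established, and no suicides were completed in the 12-week placebo-controlled portion, the experience closest in length to this trial. A reader might infer that suicidality is the gravest risk of the drug, or the only serious one singled out. The protocol makes no such ranking. Section 8.4 also warns about Crohn's disease, and Section 8.9 states: "The main risk in this study is associated with the exposure to radiation".
- **The trial is too small to compare arms on this.** True. With 25 per arm, even perfect ascertainment and no case would leave a one-sided 95% upper limit of 1 - 0.05^(1/25) = 11.3%. Section 9.1 lists no safety endpoint. The reason to ask is detection in the individual and an interpretable record, not a test.
- **Some material is not shown.** The product information, the pre-treatment chart, the participant information and the subject logbook are appendices. The chart is completed before treatment, so it is not on-treatment monitoring. The other three could tell subjects what to report, and this cannot be checked.

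**Conclusion.** The point holds in a limited form. The protocol describes suicidal ideation and behaviour as more frequent with a history of suicidality or depression and admits subjects with a stable depression history. It leaves on-treatment detection to an open question and observation at weeks 6 and 16. Sections 8.4 and 14.1 are not reconciled, and unspoken ideation is likely to be under-detected in both arms.

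The size is two scheduled enquiries in 16 weeks, neither targeted, with a longest gap of 10 weeks. No number of missed cases can be given. The conclusion rests on two assumptions: that ideation is less readily volunteered or seen than ordinary adverse events, and that the appendices not shown contain no targeted on-treatment enquiry.

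This does not touch the primary endpoint or its analysis. It is an inexpensive improvement to safety ascertainment.

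**What to change.** Reconcile Section 14.1 with Section 8.4:

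- Keep the open question, and ask it first.
- Make one exception to the rule against symptom-specific questions: a single scripted question on low mood and suicidal thoughts, put to every subject in both arms at visit 2 (as a baseline, before the first dose), visit 3 and visit 4.
- Add a row for it to the Section 7 schedule.
- Record the answer in the eCRF as a solicited item, and tabulate it by arm, apart from unsolicited adverse events.

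Handling of a positive answer is left to the investigator.

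The cost is one question at three existing visits and one eCRF field, with no added visit or staff. The drawback is that solicited events run higher than spontaneous ones, which is why the two need separate tables. The change does not shorten the 10-week gap; it makes the existing contacts more informative.

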15.1 Sample size

Derived from our investigations of vascular inflammation in psoriasis patients and control subjects, we expect a mean aortic TBR_{max} of 2.4 with a standard deviation of 0.35 in the psoriasis subjects. After successful treatment with biologic agents, we expect the MeanTBR_{max} in the psoriasis subjects to be reduced to 2.1 with SD 0.35. Based on these assumptions and an alpha-level of 0.05 we calculate that 22 psoriasis subjects in each study arm will provide a power of 80% to detect a difference between the groups. By choosing a sample size of 25 psoriasis subjects we allow for a dropout of 3 subjects at follow-up without reducing power significantly.

Trial ID (EudraCT No.): 2017-003697-14	Date: 23.02.2018	Page Version 2.3
---	------------------	---------------------

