9.1 Trial objectives and endpoints

Objectives	Endpoints
Primary objective To assess the change in aortic wall inflammation from baseline to week 16 in brodalumab treated psoriasis subjects compared to placebo.	Primary endpoint 
 Change in the average of maximum TBR values (MeanTBR_{max}) of the entire aorta from baseline to week 16
Secondary objectives To assess the change in splenic inflammation from baseline to week 16 in brodalumab treated psoriasis subjects compared to placebo. To assess the change in aortic wall subsegment inflammation from baseline to week 16 in brodalumab treated psoriasis subjects compared to placebo. To assess whether changes in skin inflammation is associated with changes in aortic wall inflammation and/or changes in splenic inflammation.	Secondary endpoint 
 Change in the spleen-to-liver ratio (SLR) based on splenic and liver mean standardised uptake values (SUV_{mean}) Change in the average of maximum TBR values (MeanTBR_{max}) of the ascending, aortic arch, descending, suprarenal, and infrarenal aorta from baseline to week 16 Association between change in PASI and change in aortic wall MeanTBR_{max} Association between change in PASI and change in SLR
Additional secondary objectives To assess the change in subcutaneous adipose tissue inflammation from baseline to week 16 in	
 Change in the average of maximum SUV values (MeanSUV_{max}) of the abdominal

Trial ID (EudraCT No.): 2017-003697-14	Date: 23.02.2018	Page Version 2.3
---	------------------	---------------------

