15.2 Trial analysis sets

A per protocol analysis set will be used as the main efficacy measure for the analysis of the endpoints at week 16.

The per protocol analysis set will be defined by excluding subjects for whom any of the following conditions apply:

- major protocol violations (e.g. did not receive treatment with investigational medicinal product)
- are known to have initiated prohibited medicine (section 11.6) during the trial
- follow-up FDG-PET/CT not completed

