15.4 Analysis of endpoints

15.4.1 Analysis of primary endpoints

The primary endpoint, change in the average of maximum TBR values (MeanTBR_{max}) of the entire aorta from baseline to week 16, will be analysed for the per protocol analysis set. The endpoint will be analysed using a repeated measurements model.

Estimates and 95% confidence intervals (CIs) or standard deviations (SDs) for the change in meanTBR_{max} and treatment differences will be presented. Values for the entire aorta and aortic subsegments will be presented. The difference in efficacy between treatment groups will be analysed. The null hypothesis of no difference in change in meanTBR_{max} between

Trial ID (EudraCT No.): 2017-003697-14	Date: 23.02.2018	Page Version 2.3
---	------------------	---------------------

brodalumab and placebo will be tested against the two-sided alternative that there is a difference.

If applicable, a supportive multivariate analysis will be performed to test the effect of the continuous covariates age, body mass index, statin treatment and categorical variables gender and smoking status on the difference in vascular FDG uptake at week 16.

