15.4.2 Analysis of secondary endpoints

The 4 secondary efficacy endpoints evaluate the impact of 16 weeks of treatment on (I) change in SLR, (II) change in the average of maximum TBR values (MeanTBR_{max}) of each aortic subsegment (ascending, aortic arch, descending, suprarenal, and infrarenal aorta), (III) association between change in PASI and change in aortic wall FDG-uptake, (IV) association between change in PASI and change in SLR.

These endpoints will be evaluated by testing the hypothesis of no difference between brodalumab and placebo. The endpoints will be analysed and presented for the per protocol analysis set.

The change from baseline to Week 16 in SLR and aortic subsegment FDG-uptake are continuous endpoints and will be analysed using a repeated measurements model.

If applicable, a supportive multivariate analysis will be performed as described in section 12.4.1.

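### The 80% power in section 15.1 is for a comparison of TBR levels, but the primary test is on change; without baseline adjustment it needs an unstated scan-to-scan correlation of about 0.5

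*Protocol*

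**What the plan says.** Section 15.1 builds the sample size on two levels. At the start, "we expect a mean aortic TBR_{max} of 2.4 with a standard deviation of 0.35 in the psoriasis subjects". After successful treatment the mean is expected to be "reduced to 2.1 with SD 0.35". With alpha 0.05 it concludes that "22 psoriasis subjects in each study arm will provide a power of 80% to detect a difference between the groups", and 25 per arm are randomised to allow for three dropouts in each.

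The primary endpoint in section 9.1 is a different quantity: "Change in the average of maximum TBR values (MeanTBR_{max}) of the entire aorta from baseline to week 16". Section 15.4.1 frames the test accordingly, as "The null hypothesis of no difference in change in meanTBR_{max} between" brodalumab and placebo, against a two-sided alternative. On method it says only: "The endpoint will be analysed using a repeated measurements model". It does not say whether baseline means are free by arm, held equal across arms, or handled through a baseline covariate. Baseline TBR is not among the covariates of the supportive analysis.

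Section 15.2 removes from the per protocol set, which is the main analysis set, any subject with "follow-up FDG-PET/CT not completed". The schedule in section 7 has FDG-PET/CT only at weeks 0 and 16.

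**The concern.** A sample size should be computed for the quantity that will be tested. The 0.35 in section 15.1 is a between-patient SD of a single TBR measurement. It is in line with the SDs of 0.31 and 0.36 that section 8.3 reports from the earlier patient-versus-control study, for which no repeat-scan figure is given. The variability of a change from baseline is another number, and it depends on how strongly a patient's two scans are correlated.

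The analysis choice decides whether this matters. Each analysed subject has exactly two scans. In that setting, a repeated measurements model with baseline means free by arm, tested on the time-by-treatment term, is the two-sample test on change scores. If the correlation is low, that test has well under 80% power with 22 per arm. If baseline is adjusted for, or its mean is constrained equal across arms, the problem disappears. The protocol leaves this choice open while stating 80% without condition.

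**Working it through.** **Inputs.** From the protocol: difference 2.4 − 2.1 = 0.3, SD 0.35, alpha 0.05, 22 per arm analysed and 25 randomised (15.1); two-sided test (15.4.1). Assumed: SD 0.35 at both scans, no change on placebo, and a correlation ρ between the scans. The protocol does not give ρ, so it is shown as a range.

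**1. The protocol's own figure.** For a two-sample comparison of levels, normal approximation:

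n = 2 × (1.960 + 0.842)² × 0.35² / 0.3² = 21.4, so 22 per arm.

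Power at 22 is 81.1% (normal) or 79.3% (noncentral t); at 25 it is 84.4% (t). The arithmetic in 15.1 is correct for comparing levels.

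**2. Change scores (baseline means free by arm).** SD of change = 0.35 × √(2(1 − ρ)). Power is by noncentral t with 2n − 2 degrees of freedom.

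**3. Baseline-adjusted (ANCOVA, or common baseline mean).** Residual SD = 0.35 × √(1 − ρ²), with 2n − 3 = 41 degrees of freedom at 22 per arm.

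| ρ (assumed) | SD of change | Change power, 22/arm | Change power, 25/arm | n/arm for 80%, change | Adjusted SD | Adjusted power, 22/arm |
|---|---|---|---|---|---|---|
| 0 | 0.495 | 50% | 56% | 44 | 0.350 | 79% |
| 0.3 | 0.414 | 65% | 71% | 31 | 0.334 | 83% |
| 0.4 | 0.383 | 72% | 77% | 27 | 0.321 | 86% |
| 0.5 | 0.350 | 79% | 84% | 23 | 0.303 | 89% |
| 0.6 | 0.313 | 87% | 91% | 19 | 0.280 | 93% |
| 0.7 | 0.271 | 95% | 97% | 14 | 0.250 | 97% |

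**4. Break-even.** At ρ = 0.5 the SD of change equals 0.35 exactly, so the level and change calculations coincide. Solving for 80% change-score power gives ρ = 0.51 at 22 per arm (0.49 by the normal approximation) and ρ = 0.44 at 25 per arm (0.41 normal). In terms of the SD of change, it must be at most 0.347 or 0.371 respectively (t).

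**5. Why adjustment does not lose.** The ratio of adjusted to change-score variance is (1 − ρ²) / (2(1 − ρ)) = (1 + ρ)/2, which is never above 1. The only cost is in degrees of freedom.

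**6. Cost of the randomisation factors.** Adding sex and four age-stratum terms leaves 36 degrees of freedom. If these factors have no effect on TBR, power at 22 per arm goes from 79.3% to 79.0% at ρ = 0, from 82.9% to 82.6% at ρ = 0.3 and from 89.3% to 89.1% at ρ = 0.5. The loss is at most 0.3 points. Any gain from age and sex cannot be quantified from the protocol.

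**7. Simulation check.** With 4,000 runs at 22 per arm and ρ = 0, 0.3, 0.5 and 0.7, change-score power was 50%, 66%, 80% and 95%; ANCOVA power was 79%, 82%, 89% and 97%. This agrees with the formulas.

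**The case against.** The strongest reply is that nothing is shown to be wrong. The 22 per arm reproduces, and sizing on the level SD is a defensible choice when the correlation is unknown: it is roughly the floor for a baseline-adjusted analysis and is conservative for change scores above ρ of about 0.5. The harm needs two things together, free baseline means and a low correlation. The first may be settled in a statistical analysis plan that was not available here. On the second, the protocol describes steps that limit measurement noise: one scanner model, an overnight fast, a fixed two-hour delay, a single observer and averaging over some 200 slices. It offers nothing in favour of a correlation of 0.3 or 0.4.

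Most of that stands, and it is why this is not called a shortfall. It does not remove the mismatch, because the protocol itself states both the 80% and a hypothesis on change, and the two do not match without a further assumption.

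Three smaller points also have substance:

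- By the t calculation, the adjusted model at 22 per arm gives 79.3% at ρ = 0, or 79.0% with the sex and age terms, and passes 80% only from ρ of about 0.14 to 0.16. The floor is therefore about 80%, by the same standard under which the protocol's own calculation gives 79.3%.
- With all 25 per arm retained, the break-even falls to 0.44.
- Section 12.3 describes a matched pairs design, and none of these figures models pairing.

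Finally, section 15.1 makes no power claim for the spleen-to-liver ratio or the aortic subsegments. Extending the adjustment to them rests on consistency and efficiency, not on the sample size.

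**Conclusion.** The concern holds as a conditional one. Section 15.1 powers a comparison of levels, while section 15.4.1 tests the difference in change. If baseline means are left free by arm, 80% at 22 per arm requires a scan-to-scan correlation of about 0.5 or more, which the protocol neither states nor supports. Over an assumed range of 0.3 to 0.7, change-score power at 22 per arm runs from 65% to 95%; at 25 per arm it runs from 71% to 97%. At 0.3, 31 per arm would be needed, against 25 randomised. Above about 0.5 the planned size is more than sufficient.

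A baseline-adjusted analysis gives about 80% or better at any non-negative correlation. These results assume SD 0.35 at both scans and no change on placebo. The trial is not shown to be underpowered. What is established is that the stated power depends on a modelling choice left open, and that one of the available choices makes it hold at almost no cost.

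**What to change.** - **Section 15.4.1:** name the primary model. Either use ANCOVA of week-16 MeanTBRmax on treatment and baseline MeanTBRmax, or a repeated-measures model with baseline means constrained equal across arms. The constraint is justified because treatment is randomised and section 12.2 places the first dose after the baseline scan. Include sex and age stratum, since they are the randomisation factors in 12.3.
- **Section 15.4.2:** use the same model where the text now says that "SLR and aortic subsegment FDG-uptake are continuous endpoints and will be analysed using a repeated measurements model".
- **Section 15.1:** say that 0.35 is the SD of the week-16 level and that the power refers to the baseline-adjusted analysis.
- **Alternative, if a change-score analysis is intended:** give an SD of change or a correlation with its source, and report power over correlations of 0.3 to 0.7.

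The cost is wording in three sections. The adjusted model spends up to six degrees of freedom (baseline, sex and four age-stratum terms), and the sex and age terms cost at most 0.3 points of power. No additional subjects, scans or data are needed. Naming the model before analysis also prevents a choice between change-score and adjusted results once the data are seen.
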